### 6.4. Recording of Adverse Events

AEs, whether observed by the Site Investigator, elicited from or volunteered by the subject, should be recorded on the AE Log and reported to the CTSDMC via AERS. AEs are to be submitted to the CTSDMC within 5 working days of the site becoming aware of the event. This will include a brief description of the experience, the date of onset, the date of resolution, the severity, and seriousness and whether the event was related to a specific procedure (procedure-related) in the research study.

Any AE ongoing at the final 7 days ( $\pm 2$  days) reporting telephone visit should be followed until resolution or stabilization, but not more than 30 days from completion of the last study procedure.

The Independent Medical Monitor (IMM) for this study will review all AEs in aggregate on a quarterly basis. The CTSDMC will provide quarterly reports to the IMM and request an evaluation. Any trends or events of concern will be provided to the Site Investigator and to the Sponsor.

### 6.5. **Responsibilities for reporting Serious Adverse Events**

- The Site Investigator will submit to the CTSDMC an AE Form through the AERS within 24 hours of his/her becoming aware of the occurrence of a SAE. The CTSDMC Project Manager will review the SAE and forward to the IMM for review.
- The following information should be supplied if available at the time of submission of the SAE study number, site number, subject number, subject age and gender, date of onset of event, event description, whether event required treatment, death and autopsy report, an identification of which criteria for a serious experience have been met, the Site Investigator's current opinion of the relationship between the event and study participation.
- The IMM will review the SAE within 2 working days of submission. The IMM will review whether the event meets the criteria for seriousness, relatedness, and expectedness. If needed, the IMM may consult with experts in the specific procedures for additional information regarding the procedures.
- The Site Investigator will comply with his/her local IRB and Radiation Safety Committee regulations regarding the reporting of AEs.

### 7. **REPORTABLE EVENTS**

The following incidents will be considered reportable events and will be reported to the CTSDMC within 24 hours of the event, or the Site Investigator's knowledge of the event.

- Change of clinical diagnosis
- Participation in an interventional/therapeutic clinical trial
- Premature withdrawal (e.g. withdrawal of consent)
- SAE
- Unanticipated problems that are not AEs
- Pregnancy (reported by female subject or female partner of a male subject)
- Death

### 8. **REFERRALS FOR MEDICAL CARE**

If a research assessment or laboratory value result reveals a clinically significant abnormality (e.g., depression, polyps requiring further assessment/biopsy, renal impairment on metabolic profile) the subject will be informed of this result and instructed to follow up with his or her primary care physician. Should there be a safety concern warranting a referral for medical or psychiatric follow-up, the Site Investigator should provide the subject with the appropriate referral as necessary.

## 9. POTENTIAL RISKS

### 9.1. Blood Sampling

Risks associated with venous blood draw include pain and bruising at the site where the blood is taken. Sometimes people can feel lightheaded or even faint after having blood drawn.

### 9.2. Lumbar Puncture

The most common risks of a LP are pain at the site and a temporary headache usually due to a small amount of CSF leakage around the needle insertion site. Lying down for a few hours after the test can make a headache less likely to occur. There is a slight risk of infection because the needle breaks the skin's surface, providing a possible portal of entry for bacteria. A temporary numbness to the legs, transient eye muscle palsy or lower back pain may be experienced. There is a small risk of bleeding in the spinal canal. Subjects will have blood drawn at Screening to test for coagulopathies.

### 9.3. DaTSCANTM SPECT Imaging

Specific potential risks for DAT SPECT imaging are as follows:

- 1. Radiation exposure from DaTSCANTM
- 2. Potential pharmacological effects of DaTSCANTM,
- **3.** Placement of an intravenous catheter. Risks associated with the intravenous injection include pain and bruising at the site where the Intravenous catheter is placed. Sometimes people can feel lightheaded or even faint after having an intravenous catheter placed.

Risks of DaTSCAN™: DaTSCAN™ is administered at radiotracer doses and is not expected to have any pharmacological or toxicological effects. The radiation of exposure from a single dose of DaTSCAN™ (85 MBq or 5 mCi) is approximately 0.4 rems. DaTSCAN™ binds to the dopamine and serotonin transporter. At pharmacologic doses DaTSCAN™ might be expected to have stimulant-like effects and affect cardiovascular responses. However, in the proposed study the estimated mass dose of DaTSCAN™ is very low - <30/pmol kg. More than 180,000 doses of the drug have been administered to human subjects.

Iodine: Prior to the DaTSCANTM injection subjects will be pretreated with SSKI (saturated solution of potassium iodide) or another thyroid protective agent standardly used in each of the

nuclear medicine imaging centers. Potential side effects from SSKI include nausea, vomiting, stomachache, diarrhea, metallic taste in the mouth, fever, headache, or acne may occur. If any of these effects persist or worsen, tell your study doctor promptly.

In addition to the known risks listed above, the imaging procedure in this study may cause unknown risks to the participant, or a developing embryo or fetus or possible risks to the future offspring of male participants. Female subjects or a female partner of a male subject who report a pregnancy within 30 days of DaTSCANTM injection will be asked to have a urine pregnancy test within 7 days of reporting the pregnancy.

### 9.4. Skin Biopsy

Risks associated with performing punch biopsies of the skin include pain and bruising at the site where the biopsy is taken. In addition, there may be blood loss at the site of the biopsy, which may require suturing. There is also a possibility of infection of the biopsy site if proper care is not provided. Sometimes people can feel lightheaded or even faint after having a skin biopsy performed.

### 9.5. Submandibular Gland Biopsy

Risks associated with performing submandibular needle biopsies include pain and bruising at the needle insertion site, bleeding or inflammation within submandibular gland, hematoma, or dysphagia. In addition, there may be blood loss at the site of the needle insertion that may require pressure dressing or in rare cases requiring cauterization. There is also the possibility of infection at the biopsy site or local numbness if a nerve is inadvertently exposed to the needle. Sometimes people can feel lightheaded or even faint after having a submandibular gland biopsy performed.

### 9.6. Flexible Sigmoidoscopy and Colon Biopsy

Risks associated with performing a flexible sigmoidoscopy and colon biopsies include pain at the site where the biopsy is taken, bleeding or inflammation within colon. In addition, there may be blood loss as a result of the biopsy procedure that may require further evaluation and in rare cases cauterization. There is also the possibility of infection at the biopsy site or perforation of the colon if the biopsy forceps extend beyond the colonic submucosa, which could require surgical repair. Sometimes people can feel lightheaded or even faint after having a flexible sigmoidoscopy and colonic biopsy performed.

## **10. STATISTICAL METHODOLOGY**

### **10.1.** Analysis Populations

### 10.1.1. Safety Analysis Population:

All safety analyses will include all subjects who were enrolled and completed at least one sampling procedure (LP, blood draw, saliva collection, skin

biopsy, colonic biopsy, or submandibular gland biopsy) as part of this study. Subjects in this analysis set will only be used for feasibility and safety analyses.

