# **3.3.** Study Population

## 3.3.1. Subject Numbers

Up to 100 subjects will be enrolled in this study. Subjects are considered enrolled in the study if they complete screening and are found to be eligible based on the inclusion and exclusion criteria. The enrollment goal for this study is 80 subjects (20 early PD not requiring dopamine replacement therapy, 20 moderate PD on dopamine replacement therapy without motor fluctuations, 20 advanced PD with motor fluctuations, 20 HC subjects) that complete at least 2 biofluid samplings (blood, saliva and CSF) and at least 2 tissue samplings (skin, colon, submandibular gland).

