### 5.1.8. **Dopamine Transporter Imaging**

Subjects will have DAT imaging procedure to measure the amount of dopamine in the brain using SPECT. All subjects will undergo SPECT imaging as part of the screening.

The SPECT imaging procedure will be performed at the individual sites using DaTSCANTM.

Upon completion of the initial (Screening) SPECT scan, the imaging core will complete a Visual Interpretation Report. For PD subjects, the Visual Interpretation Report will be provided to the clinical site to inform eligibility. For the HC subjects, the Visual Interpretation Report will not be provided to the site since it does not impact eligibility.

- If the Visual Interpretation read for a PD subject indicates that the scan does not show evidence of DAT deficit, the subject will not be eligible for participation.
- In addition, a quantitative analysis will be completed to be compared with the  $\alpha$ -syn biomarkers in the biofluid and tissue analyses.

Since this imaging information and the products used to complete the DAT SPECT scans are investigational as used in S4, it cannot provide definite information about a clinical diagnosis.

The procedure for DaTSCAN™ imaging includes:

Women of childbearing potential must have a urine pregnancy test prior to injection of DaTSCANTM. The result must be confirmed as negative prior to proceeding with the injection. Before the DaTSCANTM injection, subjects will be pre-treated with stable iodine (10 drops of a saturated solution of potassium iodide) to reduce the uptake of DaTSCANTM by the thyroid. Subjects will be injected with 3-5 mCi of dopamine transporter. Within a 4 hour (+/- 30 minute) window following the injection, subjects will undergo SPECT imaging on the camera. The data and quality assurance procedures to be employed in this study are described in the S4 Laboratory Manual.

Subjects will be monitored by study personnel for AEs on the day that a DaTSCANTM is obtained. Subjects will also be contacted by phone 7 days (±2 days) following the injection/scan to assess adverse events. These events will be reported by the Site Investigator as required to the site's Institutional Review/Ethics Boards (IRB) and to his/her Radiation Safety Committee.

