### 5.1.15.2. Adverse Events

A clinical AE is any untoward medical occurrence in a subject undergoing procedures as a participant in a clinical trial, without regard to the possibility of a causal relationship. Study site personnel will record the occurrence and nature of each subject's pre-existing conditions. During the study, site personnel will record any change in the condition(s) and the occurrence and nature of any AEs that occur during the reporting periods, which occur 7 days (±2 days) after each of the following procedures: DaTSCANTM, LP, skin biopsy, colon biopsy and submandibular gland biopsy. Site Investigators will document their assessment of the potential relatedness of each AE to study procedures or imaging agent administration via an AE form.

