#### 10.4.2. Secondary Objective:

**Feasibility & Safety:** One important secondary objective is to evaluate the feasibility and safety of obtaining multiple tissues and biofluids in an individual with PD. Feasibility will be assessed by tabulating the percentage of subjects in each group who provide complete samples. The assessment of safety will be based primarily on the frequency of procedure related AEs. All AEs will be coded using the Medical Dictionary for Regulatory Authorities (MedDRA). Procedure related AEs will be summarized by system organ class and preferred term. We will examine safety across groups in two different ways. First, the percentage of subjects who experience any procedure related AEs will be compared across groups using a chi-square test. Additionally, the rates of procedure related AEs will be compared using a Generalized Linear Model with a Poisson link.

**Compare**  $\alpha$ -syn Load Across PD Groups: Another important secondary objective is to compare the  $\alpha$ -syn load among the tissues and fluids in the PD cohort subdivided by the clinical stage of disease (early PD not requiring dopamine replacement therapy, moderate PD on

dopamine replacement therapy without motor fluctuations, advanced PD with motor fluctuations). To address this objective, trend tests (continuous or categorical, as appropriate) will be performed to assess  $\alpha$ -syn levels across the three cohorts of PD subjects.

**Compare**  $\alpha$ -syn Load with DAT Imaging: Another important secondary objective is to compare the  $\alpha$ -syn load among the tissues and fluids with disease severity based on striatal degeneration measured by DAT imaging across the PD groups in addition to comparing PD and HC groups. To accomplish this objective, each measure of  $\alpha$ -syn load will be correlated with DAT imaging data using an appropriate Generalized Linear Model.

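### The feasibility and safety set requires a completed sampling procedure, so feasibility is overstated by any enrolled subject who gave no sample, and some collected adverse events belong to no analysis set

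*Protocol*

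**What the plan says.** Protocol section 10.1.1 defines the safety analysis population: "All safety analyses will include all subjects who were enrolled and completed at least one sampling procedure". The qualifying list begins "LP, blood draw, saliva collection, skin" and continues with the skin, colon and submandibular gland biopsies. DaTSCAN is not on it. The section adds: "Subjects in this analysis set will only be used for feasibility and safety analyses". No other set is named for feasibility.

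Section 3.3.1 defines enrolment without reference to sampling: "Subjects are considered enrolled in the study if they complete screening and are found to be eligible". The ceiling is also there: "Up to 100 subjects will be enrolled in this study".

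Section 10.4.2 gives the feasibility measure: "Feasibility will be assessed by tabulating the percentage of subjects in each group who provide complete samples". Safety is measured there by the percentage of subjects with any procedure-related adverse event (AE) and by AE rates, both compared across groups.

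DaTSCAN is done at screening in all subjects (sections 4.3.1 and 5.1.8). For a PD candidate, if "the scan does not show evidence of DAT deficit, the subject will not be eligible for participation". AEs are recorded for 7 days (±2 days) "after each of the following procedures: DaTSCAN", LP and the three biopsies (section 5.1.15.2; likewise sections 4.3.5 and 6.1). For screen failures, section 10.2 provides only for demographics and reasons for failure.

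**The concern.** Feasibility and safety together form a named secondary objective, and the set used for both depends on something having been completed.

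For feasibility, this removes the clearest failures. A subject who enrols and then gives nothing is exactly what the measure should count, yet the rule takes that subject out before the percentage is formed.

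For safety, exposure begins when a procedure is started or a tracer injected, not when a sampling procedure is completed. DaTSCAN comes before enrolment and has its own AE period, but cannot bring a subject into the set. The protocol therefore collects AEs in exposed people whom its own definition leaves out of all safety analyses.

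**Working it through.** The protocol states no count or rate for this set, so there is no figure to reproduce. The check is of membership, then of direction.

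**Who is in the set**

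| Subject | Enrolled (3.3.1) | In the 10.1.1 set | AEs collected (5.1.15.2) |
|---|---|---|---|
| Study DaTSCAN, then found ineligible | No | No | Yes, after the scan |
| Enrolled, no sampling started | Yes | No | Yes, after a study scan |
| Enrolled, first LP or biopsy started but not completed, nothing else completed | Yes | No | Yes |
| Enrolled, LP or biopsy not completed, but blood or saliva collection completed | Yes | Yes | Yes |
| Enrolled, all procedures completed | Yes | Yes | Yes |

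The third row is narrow but possible: section 3.1 lets the visits occur in any order, so a biopsy visit can come first. Section 5.1.10 foresees difficulty in obtaining CSF.

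**Feasibility**

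Let N be the number enrolled, c the number with complete samples, and k the enrolled subjects who completed no sampling.

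- All enrolled: c/N.
- Section 10.1.1 set: c/(N − k).

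None of the k subjects can be among the c, so for c > 0 and k > 0 the second is always larger.

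Illustration: N = 100 is the ceiling in section 3.3.1. c = 80 is borrowed from the goal for evaluable subjects in section 3.5; evaluable there means at least 2 biofluid and 2 tissue samplings, so 80 is not a stated rate of complete samples. k is assumed.

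| k | All enrolled | Section 10.1.1 set | Difference |
|---|---|---|---|
| 2 | 80/100 = 80.0% | 80/98 = 81.6% | +1.6 points |
| 5 | 80/100 = 80.0% | 80/95 = 84.2% | +4.2 points |
| 10 | 80/100 = 80.0% | 80/90 = 88.9% | +8.9 points |

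The tabulation is by group. If the ceiling were split evenly over the four groups (100/4 = 25) and 20 in a group gave complete samples, one unsampled subject would move that group from 20/25 = 80.0% to 20/24 = 83.3%.

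**Safety**

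Let pS be the proportion with an AE among subjects in the set and pU that among the k enrolled subjects left out. The set reports pS. All enrolled subjects would give [(N − k)·pS + k·pU]/N. Take N = 100 and assume pS = 30%:

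| k | pU = 0% | pU = 30% | pU = 60% | pU = 100% |
|---|---|---|---|---|
| 5 | 28.5% | 30.0% | 31.5% | 33.5% |
| 10 | 27.0% | 30.0% | 33.0% | 37.0% |

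For example, k = 5 and pU = 60% gives (95 × 0.30 + 5 × 0.60)/100 = 31.5%. The reported 30% is too low when pU exceeds pS and too high when it is smaller. The sign is not fixed.

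**The case against.** A reader might infer that failed attempts in general are dropped and that feasibility and safety both look too good. The protocol does not support either.

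- **Failed attempts.** Blood draw and saliva collection each qualify, and section 4.3.2 lists both before LP and skin biopsy at the same visit. One of them completed keeps a subject with a failed LP or biopsy in the set. Only a subject who completed nothing is lost. Nor is completion plainly the same as yield: a finished biopsy with little or no tissue can be read as completed.
- **Safety bias.** Subjects who had only a DaTSCAN faced one exposure and no biopsy. If few of them had AEs, leaving them out raises the AE percentage.

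Four further points deserve weight. Section 10.4.2 does not name the feasibility denominator; using the section 10.1.1 set follows from its being the only one assigned to feasibility. Leaving DaTSCAN off the qualifying list fits an objective about obtaining tissues and fluids, and a scanned but ineligible PD candidate belongs to none of the compared groups. Those subjects' AEs still reach oversight: the medical monitor reviews all AEs quarterly (section 6.4), and serious events are reported within 24 hours (section 6.5). Finally, this is a secondary objective of an exploratory study, and the number of unsampled subjects is unknown.

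These arguments limit the point without removing it. Section 10.1.1 states a rule rather than leaving one to be set later, and monitoring during the study does not put an event into the reported safety analysis.

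**Conclusion.** The point holds in two parts. Feasibility is overstated whenever an enrolled subject completes no sampling, given that the section 10.1.1 set is the denominator. The direction is certain; the size is not. Under the assumed counts it is 1.6 to 8.9 points for 2 to 10 unsampled subjects out of 100. Safety reporting is incomplete: AEs after a study DaTSCAN in ineligible or never-sampled subjects, and AEs from a started but uncompleted procedure in a subject who completed no other, have no analysis set. No direction can be claimed for the AE percentage. The protocol gives no expected number for any of these subjects, so k, c, pS and pU are all assumptions. The wording should be corrected, since the objective concerned is a named one.

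**What to change.** Amend sections 10.1.1 and 10.4.2 as follows.

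1. Feasibility: use all enrolled subjects in each group as the denominator.
2. Safety set: all subjects in whom any study procedure was started, including a DaTSCAN injection given for this study. A PPMI scan reused under section 3.1 involves no new exposure and does not count.
3. Tabulate AEs per procedure, with the subjects in whom that procedure was started as the denominator.
4. Report DaTSCAN AEs in screen failures separately, so that they do not dilute the group comparison of sampling-procedure AEs.

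The cost is wording and a few tables. The AE data are already collected. The vital signs that section 5.1.15.4 requires before and at the end of DaTSCAN, LP and each biopsy help to identify procedures that were started but not completed. The downside is that reported feasibility may be slightly less favourable.

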#### 10.1.2. Synuclein Burden Population:

For analyses examining  $\alpha$ -syn burden across groups, all subjects with relevant data for all comparisons will be used in the  $\alpha$ -syn burden analyses.

### **10.2.** Descriptive Statistics

Descriptive statistics will be generated for important demographic (age, gender, race, ethnicity) and clinical characteristics (duration of disease, MDS-UPDRS total and motor score, Hoehn and Yahr, Schwab and England, MOCA, SCOPA-AUT). For continuous variables, the mean, standard deviation, median, minimum, and maximum will be displayed for each subset of the PD cohort (20 early PD not requiring dopamine replacement therapy, 20 moderate PD on dopamine replacement therapy without motor fluctuations, 20 advanced PD with motor fluctuations), the PD subjects overall, and the HC cohort. For categorical variables, the percentage of subjects falling in each category will be displayed for each of these groups. Comparisons across the groups will be performed using t-tests and/or chi-square tests, as appropriate.

Demographic variables of screen failure subjects, and reasons for screen failures, will be summarized for all subjects who are screened but not randomized into the study.

## 10.3. Study Outcome Measures

### 10.3.1. **Biofluid** α-syn levels:

Whole blood, serum, plasma, saliva, and CSF  $\alpha$ -syn will be analyzed using the most optimal, currently available, quantitative and semi-quantitative assays. The outcome will be expressed as a concentration of total  $\alpha$ -syn and other  $\alpha$ -syn species or a ratio of specific species to total levels.

### 10.3.2. α-syn deposits in skin:

 $\alpha$ -syn burden in skin biopsies will be expressed as 1) simply positive or negative, i.e. whether any two slides are positive out of all examined 2) by total percentage of slides examined that are positive 3) by site of highest density of positive  $\alpha$ -syn fibers.

### 10.3.3. α-syn deposits in submandibular gland:

 $\alpha$ -syn burden in the submandibular tissue will be expressed as 1) simply positive or negative, i.e. whether any two slides are positive out of all examined 2) by total percentage of slides examined that are positive 3) by site of highest density of positive  $\alpha$ -syn fibers.

